#### 9.4.6.3.2.2 Gout Flare Treatment

An increase in gout flares is frequently observed upon initiation of ULT, including pegloticase. Subjects will be instructed to contact the site within 12 hours of the onset of symptoms. Gout flares will be confirmed through questioning or direct observation, as detailed in Section 9.5.4.10. All subjects who experience a gout flare during the study will be prescribed anti-inflammatory treatment (e.g., corticosteroids, colchicine, and intra-articular steroid injections), as is clinically indicated or deemed necessary on an individual basis at the discretion of the investigator (Becker, 2019). Pain medications for gout flare should be administered according to standard of care as is clinically indicated or deemed necessary on an individual basis at the discretion of the investigator. All medications should be documented on the concomitant medication eCRF.

Colchicine can be prescribed. The precise dose and regimen of colchicine should be individualized for each subject based on renal function and gastrointestinal intolerance by the Investigator and documented on the concomitant medication eCRF.

#### 9.4.6.3.2.3 Infusion Reaction Treatment

Subjects must be monitored closely for signs and symptoms of IRs. In the event of an IR, the infusion should be slowed, or stopped, and restarted at a slower rate at the discretion of the Investigator. If a serious IR occurs, the infusion should be discontinued and treatment should be provided, as needed.

If a subject experiences an AE suspected to be an IR:

- A physical examination will be performed to capture medically relevant details, including, but not limited to, a thorough dermatologic examination for detection of erythema, urticaria (hives), or peri-oral or lingual edema; a chest examination for breath sounds, stridor or wheezing; and a cardiac examination with attention to the possibility of an irregular heartbeat;
- Vital signs (sitting or supine blood pressure, heart rate, respiratory rate, and body temperature) will be captured at least every 30 minutes until the resolution or stabilization of the AE;
- 12-lead ECG will be performed;
- A serum sample will be collected in a serum-separating tube at that time or at the subsequent visit. The sample will be centrifuged, frozen at -20°C or colder, and stored for the batch shipment to a Horizon designated laboratory for evaluation of pegloticase antibodies at a future date.

If, in the Investigator's opinion, the subject is experiencing an anaphylactic reaction (see Section 9.5.4.1.1.5), pegloticase should be immediately discontinued. Any incidence of anaphylaxis should be reported as an SAE.

The Investigator may administer any medically indicated pharmacologic agent or procedure intended to relieve symptoms (CAUTION: no other drugs can be mixed in the pegloticase infusion bag). Signs

and symptoms of the AE and drugs given for treatment are to be recorded in the medical record and in the eCRF.

After the first incidence of an IR that does not meet the criteria of anaphylaxis (see Section 9.5.4.1.1.5) or does not meet serious criteria, the Investigator may elect to initiate the next infusion at a slower rate. All changes to infusion rate or dilution, and drugs given for prophylaxis or treatment, are to be recorded in the medical record and in the eCRF.

#### **9.4.7 Method of Assigning Subjects to Pegloticase**

Medidata Randomization and Trial Supply Management (RTSM) will be used to assign subjects specific pegloticase kit numbers.

Specific procedures for accessing and assigning study drug through Medidata are contained in the study procedures manual.

#### **9.4.8 Blinding**

Because all subjects will receive pegloticase, this study drug will be administered without blinding and all subjects, Investigators and site personnel will know that all subjects are receiving pegloticase.

#### **9.4.9 Prior and Concomitant Therapy**

Medication history (i.e., prior medications) will include all prior gout medications, starting at the time of diagnosis and up to the Screening Visit, and all other medications taken from 1 year prior to the Screening Visit.

Concomitant medications are defined as drug or biological products other than the study drugs (or prior gout medications) taken by a subject from Screening through the Post-Treatment Follow-up Visits. This includes other prescription medications (including preventive vaccines), over the counter medications, herbal medications, vitamins, and food supplements.

Information about prior and concomitant medications, including those used for any duration to treat an AE, will be collected on source documents and the appropriate eCRFs at each visit. The generic name of the medication, indication, dose, unit, frequency, route of administration, and start and stop dates will be recorded.

Subjects will be directed to discontinue current ULT prior to initiation of pegloticase therapy as per the current package insert. Other medications used at the time of study initiation may be continued at the discretion of the Investigator.

#### **9.4.10 Restricted Medications**

Subjects should not receive the following medications from the time of Screening through the end of pegloticase treatment:

- Oral ULTs including allopurinol, febuxostat, probenecid, lesinurad, or other ULT for gout; Re-introduction of oral ULTs should not start until after the End of Pegloticase Visit (or End of Study) laboratory tests are collected.

- Any PEG-conjugated drug; nor
- Any other investigational agent

#### **9.4.11 Treatment Compliance**

At study visits, the subject will be asked a Yes/No question whether gout flare, and IR prophylaxis were administered.

Pegloticase will be administered at the study site by trained personnel. The date and times of infusion start and stop (inclusive of the 10 mL flush) will be recorded.

#### **9.4.12 Contraception Requirements**

Women of childbearing potential (including those with an onset of menopause <2 years prior to Screening, non-therapy-induced amenorrhea for <12 months prior to screening, or not surgically sterile [absence of ovaries and/or uterus]) must agree to use a medically approved form of birth control during their participation in the study.

### **9.5 Efficacy, Quality-of-Life, Pharmacokinetic, and Safety Variables**

The Schedule of Assessments is provided in Section 2.1.

#### **9.5.1 Efficacy Variables**

Efficacy will be assessed by sUA levels, tophus size and resolution, urate deposition volume (using DECT), blood pressure, renal function, gout flare and physician global assessment of gout. Assessment of BP, eGFR and UACR are described in Section 9.5.1.4. These variables are also part of safety assessments.

##### **9.5.1.1 Serum Uric Acid**

Serum samples for measurement of sUA levels will be collected at the Screening Visit, prior to and after the end of each pegloticase infusion during the pegloticase treatment period. .

Additional serum samples for sUA levels will be collected at non-infusion Visits at Weeks 21 and 23, the End-of-Pegloticase-Infusions Visit (if applicable), the Week 24/End-of-Study/Early Termination Visit and the 3-month Follow-up Visit. Subjects with an sUA level >6 mg/dL at

2 consecutive study visits beginning with the Week 2 Visit will discontinue pegloticase and will be encouraged to continue study participation through Week 24.

Two separate samples/tubes of blood should be collected within 48 hours prior to the pegloticase infusion if the previous visit's pre-infusion sUA value is > 6 mg/dL (except on Day 1 when only 1 pre-infusion sample is required for the central laboratory). One sample/tube will be assessed by the site's local laboratory to be used for on-study subject management; pre-infusion sUA results must be reported by the local or central laboratory prior to each pegloticase infusion if the previous visit's pre-infusion sUA value is > 6mg/dL. If a local laboratory sample is drawn (within 48 hours prior to the pegloticase infusion), a sample for the central laboratory will be drawn prior to the pegloticase

infusion on the day of the visit. The second sample/tube will be sent to the central laboratory for analysis and recording in the database. See the Laboratory Manual for instructions for alternate scenarios.

A subject with a sUA level >6 mg/dL (based on the local or central laboratory) at 2 consecutive study visits, beginning with the Week 2 Visit, will be discontinued from pegloticase treatment.

Samples that result in discordant results between local and central laboratories will be evaluated and discussed with the Investigator and the Sponsor's Medical Monitor on a case-by-case basis to determine whether the subject should continue on study or discontinue.

Hand held uric acid measurement devices maybe provided to measure subject uric acid levels in real time. If hand held devices are provided, blood uric acid levels obtained from the device prior to pegloticase infusion will NOT be used to manage pegloticase treatment.

#### **9.5.1.2 Hand Held Uric Acid Measurement Device**

Select sites and patients may be provided with FDA approved devices to measure subject uric acid levels using a hand-held device. Results will be collected pre-infusion and post-infusion and used for exploratory uses only. No in-study treatment decisions will be made based upon the data generated with the hand held device.

#### **9.5.1.3 Physician Global Assessment**

The physician global assessment will be collected at Screening and prior to pegloticase infusion at the Day 1 and Week 6, 14, 20, End-of-Pegloticase-Infusions Visit (if applicable), and the Week 24/End-of-Study/Early Termination Visit (Section 2.1). The physician will respond to the statement, "Considering the subject's overall health related to gout, rate their gout overall" using a numeric rating scale ranging from 0 (excellent) to 10 (very poor) (see Appendix 17.3).

For a given subject, if possible, the same qualified Investigator should perform the assessment at each time point.

#### **9.5.1.4 Dual-energy Computed Tomography (DECT)**

For sites with DECT capability, DECT will be obtained between the Screening Visit (after all eligibility criteria have been confirmed) and the Day 1 Visit, the Week 14 Visit, the

End-of-Pegloticase-Infusions Visit (if applicable), and at the Week 24/End-of-Study/Early Termination Visit. The DECT may be completed within  $\pm 7$  days of the Week 14 and Week 24 Visits.

Subjects who end pegloticase infusions prior to Week 24 should follow the scheduled timepoints but avoid a repeat DECT scan within 6 weeks of a prior scan (detailed guidance is provided within the imaging manual).

Images will be obtained for the knees, hands/wrists and feet/ankles. The imaging will be performed by a study-specific, qualified radiologist.

### 9.5.1.5 Digital Photography

Digital photography of hands and feet will be completed at Screening, Day 1, Week 14, the End-of-Pegloticase-Infusions Visit (if applicable), the Week 24/End-of-Study/Early Termination Visit, and the 3-month Post-Treatment Follow-up Visit. Other anatomical sites with large tophi may be photographed in addition to the hands and feet at the Investigator's discretion.

The sponsor or designee will provide digital photography equipment to each site for photography of the hands and feet.

Details on the digital photography, including source documentation and eCRF requirements will be provided in the Study Reference Binder.

#### 9.5.1.5.1 Assessment of Individual Tophi Response

All measurable tophi will be measured bi-dimensionally (using the longest diameter and the longest perpendicular to that diameter) and the response of each individual tophus will be categorized according to the change from baseline in area of each tophus at each visit as follows:

- Complete Response (CR) – A 100% decrease in the area of the tophus;
- Marked Response (MR) – At least a 75% decrease in the area of the tophus;
- Partial Response (PR) - At least a 50% decrease in the area of the tophus;
- Stable Disease (SD) – Neither a 50% decrease nor a 25% increase in the area of the tophus can be demonstrated;
- Progressive Disease (PD) – A 25% or more increase in the area of the tophus; or
- Unable to Evaluate (UE) –The tophus cannot be accurately measured for any reason at any given post-baseline time point (e.g., image missing or of poor quality, obvious infection of the tophus).

Each individual unmeasured tophus will be semi-quantitatively assessed based upon the impression of the central reader using the following guideline:

- Complete Response - the disappearance of the tophus;
- Improved - An approximate 50% or more reduction from baseline in the size of the tophus;
- Stable Disease – Neither improvement nor progression from baseline can be determined;
- Progressive Disease - An approximate 50% or more increase from baseline in the area of the tophus; or
- Unable to Evaluate - The tophus cannot be assessed for any reason at any given post-baseline time point (e.g., image missing or of poor quality, or obvious infection of the tophus).

The overall response for a subject will be based upon the best response among all tophi (including measurable and unmeasurable) for that subject (e.g., if any one tophus shows complete response, the

overall response is Complete Response). If any single tophus shows progression, or if a new tophus appears during the study, the overall response for that subject will be Progressive Disease, regardless of the response of any other tophi.

### 9.5.2 Quality of Life Assessment

The HAQ (Appendix 17.2) including the HAQ-DI, pain and health scales, will be administered at Screening and prior to the pegloticase infusion at the Day 1 Visit, the Week 6 and 14 Visit, the End-of-Pegloticase-Infusions Visit (if applicable), the Week 24/End-of-Study/Early Termination Visit, and the 3-month Post-Treatment Follow-up Visit (Section 2.1).

The HAQ-DI is a self-report functional status instrument that can be filled out by a subject in less than 5 minutes and requires 1 minute to score. The index measures disability over the past week by asking a total of 20 questions covering 8 domains of function: dressing and grooming, arising, eating, walking, hygiene, reach, grip, and usual activities. There are at least 2 questions in each domain and the 8 domains represent a comprehensive set of functional activities. The HAQ-DI is calculated by scoring the answer to each question in the HAQ from 0 to 3, with 0 representing the ability to do without any difficulty, and 3 representing inability to do. Any activity that requires assistance from another individual or requires the use of an assistive device raises a 0 or 1 score to a 2. The highest score for each of the 8 domains is summed (range from 0 to 24) and divided by 8 to yield, on a scale with 25 possible values, a Functional Disability Index with a range from 0 to 3. The disability index is based on the number of domains answered and is computed only if the subject completes answers to at least 6 domains (Bruce and Fries, 2003).

The HAQ pain scale consists of a doubly-anchored, horizontal visual analog scale (VAS), that is scored from 0 (no pain) to 100 (severe pain). Subjects are asked to rate the severity of the pain they have had because of illness in the past week by placing a vertical mark on the VAS.

### 9.5.3 Pharmacokinetic and Anti-drug Antibody Measurements

Serum samples for PK analysis of pegloticase will be collected after the end of infusion on Day 1 (prior to discharge); prior to the pegloticase infusion and after the end of the infusion (prior to discharge) at Weeks 2, 6, 14, and 22. Additional PK samples will be collected at the Week 21 Visit, the End-of-Pegloticase-Infusions Visit (if applicable), and the Week 24/End-of-Study/Early Termination Visit.

Serum samples for evaluation of anti-PEG and anti-uricase IgG antibodies will be collected prior to the pegloticase infusion on Day 1 and at the Week 2, 6, 14, 22 Visits, the End-of-Pegloticase-Infusions Visit (if applicable), the Week 24/End-of-Study/Early Termination Visit, and the 3-month Post-Treatment Follow-up Visit.

Each sample collection date and time will be recorded in source documents and the eCRF.

Detailed instructions regarding blood sample timing and handling are provided in the Laboratory Manual.

#### **9.5.4 Safety Variables**

Safety will be assessed via AE and concomitant medication use monitoring, physical examinations, vital signs, clinical safety laboratory evaluations (hematology, chemistry, urine albumin:creatinine ratio, eGFR), pregnancy testing (if applicable), electrocardiograms (ECGs), and AEs of special interest (i.e., IRs, anaphylaxis, gout flares, and CV events) and incidence of biopsy confirmed renal rejection.

##### **9.5.4.1 Adverse Events**

###### **9.5.4.1.1 Definitions**

###### **9.5.4.1.1.1 Adverse Event Definition**

As defined by the ICH, an AE is any untoward medical occurrence in a clinical study subject administered a medicinal (investigational or non-investigational) product, whether or not the event is considered related to the study drug. An AE is therefore any unfavorable and unintended sign (including an abnormal laboratory finding), symptom, or disease (new or exacerbated) temporally associated with the use of the study drug. This includes any occurrence that is new in onset or aggravated in severity or frequency from the baseline condition, or abnormal results of diagnostic procedures, including laboratory test abnormalities.

Examples of an AE include:

- Conditions newly detected or diagnosed after the signing of the ICF, including conditions that may have been present but undetected prior to the start of the study;
- Conditions known to have been present prior to the start of the study that worsen after the signing of the ICF;
- Signs, symptoms, or the clinical sequelae of a suspected drug interaction; and
- Signs, symptoms, or the clinical sequelae of a suspected overdose of either investigational product or a concomitant medication (overdose per se should not be reported as an AE).

Issues that will not be considered an AE include:

- Conditions present at the start of the study, should be recorded as medical history;
- Medical or surgical procedures (e.g., endoscopy, appendectomy; however, a condition that leads to a procedure is an AE if it qualifies according to the definitions above);
- Situations where an untoward medical occurrence did not occur (e.g., social, diagnostic, elective, or convenience admission to a hospital);
- Fluctuations of pre-existing disease(s) or condition(s) present or detected at the start of the study that do not represent a clinically significant change from baseline; and

- Abnormal laboratory or test findings that are not assessed by the Investigator as a clinically significant change from baseline.

AEs are divided into the categories “serious” and “non-serious.” This determines the procedures that must be used to report/document the AE.

#### 9.5.4.1.1.2 Serious Adverse Event Definition

Based on ICH guidelines, an SAE is any untoward medical occurrence that at any dose:

- Results in death;
- Is life threatening;  
NOTE: The term ‘life threatening’ in the definition of ‘serious’ refers to an event in which the subject was at risk of death at the time of the event. It does not refer to an event that hypothetically might have caused death if it were more severe, prolonged, or untreated.
- Requires hospitalization or prolongation of existing hospitalization;  
NOTE: Hospitalization signifies that the subject has been admitted to the hospital as an inpatient for any length of time. Treatment on an emergency, outpatient basis for an event not fulfilling any of the definitions of SAEs and not resulting in hospital admission does not qualify for this category, but may be appropriately included in category g (see below).  
Complications that occur during hospitalization are usually AEs. If a complication prolongs hospitalization or fulfills any other serious criterion, the event will be considered as serious. When in doubt as to whether ‘hospitalization’ occurred, consult the Sponsor’s Medical Monitor.  
Hospitalization will not be considered an AE in and of itself. It will be considered an outcome of an AE. Therefore, if there is no associated AE, there is no SAE. For example, hospitalization for elective or pre-planned treatment of a pre-existing condition that did not worsen from baseline will not be considered an AE.
- Results in persistent or significant disability/incapacity;  
NOTE: The term disability means a substantial disruption of a person’s ability to conduct normal life functions. This definition is not intended to include experiences of relatively minor medical significance, such as uncomplicated headache, nausea, vomiting, diarrhea, influenza, and accidental trauma (e.g., sprained ankle) that may temporarily interfere with or prevent everyday life functions but do not constitute a substantial disruption.
- Is a congenital anomaly/birth defect;
- Is a suspected transmission of any infectious agent via a medicinal product; and
- Is an important medical event.  
NOTE: Medical and scientific judgment should be exercised in deciding whether expedited reporting as serious is appropriate in other situations; specifically, important medical events that may not be immediately life threatening or result in death or hospitalization but may jeopardize the subject or may require medical or surgical intervention to prevent one of the other outcomes listed in the above definition. These should usually be considered serious. Examples of such events are invasive cancers, intensive treatment in an emergency room or at home for allergic bronchospasm, blood dyscrasias,

or convulsions that do not result in hospitalization, or development of drug dependency or drug abuse. If in doubt as to whether or not an event qualifies as an ‘important medical event,’ consult the Sponsor’s Medical Monitor.

#### 9.5.4.1.1.3 Non-Serious Adverse Event Definition

AEs that do not result in any of the outcomes listed in Section 9.5.4.1.1.2 are considered non-serious.

#### 9.5.4.1.1.4 Unexpected Adverse Event Definition

An AE or suspected adverse reaction is considered unexpected if it is not listed in the Reference Safety Information section of the Investigator’s Brochure or is not listed with the specificity or severity that has been observed. Unexpected, as used in this definition, also refers to AEs or suspected adverse reactions that are mentioned in the Reference Safety Information as occurring with a class of drugs or as anticipated from the pharmacological properties of the drug, but are not specifically mentioned as occurring with the particular drug under investigation.

#### 9.5.4.1.1.5 Adverse Events of Special Interest

AEs of special interest include IRs, anaphylaxis, gout flares, and CV events. An external adjudication committee will adjudicate the AESIs of IR, anaphylaxis and CV events.

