3-month follow up visit. In the event of an AE suspected to be an infusion reaction, a sample will be collected at that time or at the subsequent visit for future evaluation of antibodies.

Safety assessments, including monitoring and recording of all AEs, whether or not drug-related, measurement of vital signs, physical examinations, monitoring of hematology and blood chemistry and acute renal rejection, will be performed.

An independent adjudication committee will review reported events of infusion reactions, cardiovascular events and anaphylaxis.

An overview of the study design is presented in the schematic below.

Screening 	Treatment Period 	Follow Up 
Screen (up to 35 days)	Pegloticase 8 mg IV every 2 weeks D1  W2 W4 W6 W8 W10 W12 W14 W16 W18 W20 W21  W22 W23  W24 	30-days post-last pegloticase infusion and 3 months after End-of-Pegloticase Infusions Visit or Wk 24 End-of-Study/Early Termination Visit

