Week 24/End-of-Study /Early Termination Visit and the 3-month follow up visit. In the event of an AE suspected to be an IR, a sample will be collected at that time or at the subsequent visit for future evaluation of ADAs.

Safety assessments, including monitoring and recording of all AEs, whether or not drug-related, measurement of vital signs, physical examinations, and monitoring of hematology and blood chemistry and acute renal rejection, will be performed.

An independent external adjudication committee will review reported events of IRs, major CV events and anaphylaxis.

An overview of the study design is presented in the schematic below, and details of study activities are provided in Section 2.1.

Figure 9.1 Schematic of Study Design

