### **Cardiovascular Events**

Cardiovascular AEs will be collected as part of the AE recording. External adjudication will be conducted for selected CV events. Refer to the Adjudication Committee Charter for the detailed definition.

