#### 9.6.1.5 Safety and Tolerability Endpoints

Safety and tolerability objectives are:

- Overall AE/SAE profile;
  - Incidences of AESI: IRs, anaphylaxis, gout flares, cardiovascular events;
- Laboratory tests;
- Vital signs and physical examination; and
- Incidence of renal rejection (biopsy proven).

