### 9.6.7 Safety Analysis

Treatment-emergent AEs are defined as events with an onset date on or after the start of the first pegloticase infusion through 30 days after the last dose of pegloticase. AEs that occur more than 30 days after the last dose of pegloticase through the 3-month follow-up visit will also be summarized.

The number and percentage of subjects experiencing AEs will be summarized by system organ class and preferred term. Summaries by maximum severity and relationship to study drug will also be provided. SAEs and AEs leading to discontinuation of study drug will be presented by system organ class and preferred term. The proportion of subjects with each AESI will also be summarized.

Laboratory test results will be summarized by study visit and change from baseline. Shift tables for laboratory parameters by Common Terminology Criteria for Adverse Events grade will be presented. Laboratory test results will also be classified relative to the normal reference range (normal, low, or high).

Vital signs, including BP, respiratory rate, temperature, and heart rate, will be summarized by study visit and change from baseline.

Prior and concomitant medications will be summarized and/or included in the data listings.

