#### 12.3.3.2. *Cardiovascular Events*

Cardiovascular events will include Major Adverse Cardiovascular Events (MACE).

Any MACE including Non-fatal myocardial infarction, non-fatal stroke, cardiovascular death, and congestive heart failure.

- For cardiovascular death:
  - Standardized MedDRA Queries (SMQ): Myocardial infarction, Ischaemic Central Nervous System (CNS) Vascular conditions; Haemorrhagic central nervous system vascular conditions, Central nervous system vascular disorders, not specified as haemorrhagic or ischaemic, Embolic and thrombotic events (arterial, venous, vessel type unspecified and mixed arterial and venous), Cardiac failure, shock-associated conditions, Torsade de pointes/QT prolongation, Arrhythmia related investigations, signs and symptoms, Cardiomyopathy, Supraventricular tachyarrhythmias (narrow), Ventricular tachyarrhythmias (narrow), Conduction defects
  - All PTs under SOC of Cardiac disorders
  - HLGT Aneurysm
- For non-fatal myocardial infarction: SMQ Myocardial infarction
- For non-fatal stroke: SMQ: Ischaemic Central Nervous System (CNS) Vascular conditions; Haemorrhagic central nervous system vascular conditions; Central nervous system vascular disorders, not specified as haemorrhagic or ischaemic
- Congestive heart failure: SMQ Cardiac failure

Cardiovascular events will be tabulated only if 5 or more subjects have experienced a cardiovascular event or have an event adjudicated as a cardiovascular event. Using the safety population, cardiovascular events will be summarized by MedDRA SOC and PT, adjudicated as well as any identified by investigator.

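### The SAP's cardiovascular AESI summary has a narrower search than the protocol's term and is tabulated only if five subjects have an event, so the incidence can be understated or left untabulated

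*Protocol*

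**What the plan says.** **The term and the promise.** Protocol 9.5.4.1.1.5: "AEs of special interest include IRs, anaphylaxis, gout flares, and CV events". Protocol 9.6.1.5 makes this a safety endpoint: "Incidences of AESI: IRs, anaphylaxis, gout flares, cardiovascular events". Protocol 9.6.7 sets the analysis: "The proportion of subjects with each AESI will also be summarized". No minimum count is attached. SAP 5.5 and 12.3.3 keep the unrestricted term.

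**The SAP's working definition.** SAP 12.3.3.2 begins "Cardiovascular events will include Major Adverse Cardiovascular Events (MACE"). It then gives MedDRA searches for four components: non-fatal myocardial infarction, non-fatal stroke, congestive heart failure and cardiovascular death. Each non-fatal component gets its own SMQ or small set of SMQs. The wide list (arrhythmia, conduction, QT, embolic and thrombotic and cardiomyopathy SMQs, the whole Cardiac disorders SOC, and aneurysm) sits under cardiovascular death. The section adds that the summary covers adjudicated events and any that the investigator identified. It also makes the table conditional on at least five subjects having an event.

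**Adjudication.** The Protocol synopsis says "An independent adjudication committee will review reported events of infusion reactions, cardiovascular events and anaphylaxis". Section 9.1 says the committee "will review reported events of IRs, major CV events and anaphylaxis". Section 9.5.4.1.1.5 says "An external adjudication committee will adjudicate the AESIs of IR, anaphylaxis and CV events", and its paragraph on cardiovascular events says "External adjudication will be conducted for selected CV events", leaving the definition to the committee charter.

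**Recorded changes.** SAP 14 lists the renamed populations and the rephrased laboratory and vital-sign endpoints. It mentions neither the cardiovascular searches nor the threshold.

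**The concern.** The protocol commits to a subject-level proportion for cardiovascular events. A programmer working from SAP 12.3.3.2 has search terms only for MACE components. A fatal ventricular arrhythmia would be found by those terms, but the same arrhythmia survived would not, nor would a non-fatal venous thromboembolism. The five-subject rule then removes the table at any count below a quarter of the planned sample. In a 20-subject study of transplant recipients, a reader looking for the cardiovascular AESI incidence could find a figure that omits some subjects, or no figure. The differing adjudication wording adds to this, because the adjudicated events are one of the routes into the summary.

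**Working it through.** The documents state no cardiovascular event rate, so there is no plan figure to reproduce. The check is a comparison of text, followed by arithmetic at the planned N = 20 (Protocol 9.6.9).

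**1. Adjudication scope, side by side**

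| Place | Cardiovascular events adjudicated |
|---|---|
| Protocol synopsis | unqualified |
| Protocol 9.1 | major |
| Protocol 9.5.4.1.1.5, opening | unqualified |
| Protocol 9.5.4.1.1.5, cardiovascular paragraph | selected, per charter |
| Protocol 9.5.5 | unqualified, with reference back to 9.5.4.1.1.5 |

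**2. Routes by which a non-fatal event outside infarction, stroke and heart failure could enter the summary**

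- SAP search terms: none apply, because the wide list is attached to death.
- Adjudication: depends on which scope in step 1 is followed, and on a charter that is not among the documents.
- Investigator identification: possible, since cardiovascular AEs are collected with all other AEs. Footnote 10 of the schedule of assessments describes an investigator prompt for possible infusion reaction or anaphylaxis. No cardiovascular prompt is described.

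**3. Effect of a missed subject**

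Each missed subject changes the proportion by 1/20 = 5 percentage points. For k missed subjects the shortfall is 5k points. The narrower search can lower the count or leave it unchanged; it cannot raise it. The documents do not give k, and k = 0 is possible.

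**4. Effect of the threshold**

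The table needs 5/20 = 25% of subjects. With X subjects having a counted event, true subject-level rate p (assumed) and independent subjects:

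P(no table) = P(X ≤ 4) = Σ C(20,x) p^x (1−p)^(20−x), x = 0 to 4.

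At p = 0.10: 0.1216 + 0.2702 + 0.2852 + 0.1901 + 0.0898 = 0.957 after rounding.

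Subtracting P(X = 0) = (1−p)^20 gives the chance that events occur but are not tabulated.

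| Assumed p | P(no table) | P(X = 0) | P(1 to 4 subjects, no table) |
|---|---|---|---|
| 5% | 99.7% | 35.8% | 63.9% |
| 10% | 95.7% | 12.2% | 83.5% |
| 15% | 83.0% | 3.9% | 79.1% |
| 20% | 63.0% | 1.2% | 61.8% |
| 25% | 41.5% | 0.3% | 41.2% |

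The largest result left untabulated is 4/20 = 20%. Its exact (Clopper-Pearson) 95% interval is 5.7% to 43.7%. The SAP plans no interval for AE incidence; it is given here only to show which true rates such a result would be compatible with.

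**5. The two restrictions combine**

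Suppose three subjects have MACE and two others have only non-fatal cardiovascular events outside the three searches. Counting all of them gives 3 + 2 = 5, and the table is produced. If the other routes miss the two, the count is 3 and it is not.

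**The case against.** The strongest reply has four parts.

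- SAP 12.3.3.2 says that cardiovascular events include MACE, not that they are confined to MACE, and it names adjudicated and investigator-identified events as well. This stands. It is why undercounting is a possibility and not a demonstrated result.
- The general tables already carry the information. SAP 12.3.2 summarizes all TEAEs by SOC and PT and counts a subject at most once per SOC, so the Cardiac disorders row is itself a subject-level count. There is also an overall AESI line and an AESI listing. This stands in part. The SAP's own list extends beyond that SOC, and events coded elsewhere are not combined with it. The overall AESI line pools all AESI types and relies on the same unclear cardiovascular term.
- The adjudication wording may be loose drafting and not conflict. Section 9.5.5 refers back to the section containing the restriction to selected events, major and selected may mean the same thing, and the charter may settle the matter. That is fair, but the charter is not available, and the synopsis and the opening of 9.5.4.1.1.5 carry no qualifier.
- The protocol never defines cardiovascular events by SMQ or SOC, so the wide list is not the protocol's definition, and giving an undefined term a working definition need not be a change from protocol. This stands for the search terms. It does not answer the threshold, which conflicts with an unconditional commitment in Protocol 9.6.7.

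A reader might infer that the SAP's figure is certainly too low, or is a different endpoint from the protocol's. The documents do not support either. Nor would a contrast of small counts, such as one subject against three, show what the SAP would report: neither count reaches five, so neither would be tabulated.

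**Conclusion.** The point holds as one of definition and reporting. The specified searches for non-fatal events are narrower than the protocol's term, the five-subject rule contradicts the protocol's promise of a proportion for each AESI, and SAP 14 discloses neither. The cardiovascular AESI incidence can be understated by 5 percentage points per missed subject. The number missed cannot be determined, and is zero if no such event occurs or if adjudication or the investigator captures it. The threshold's effect is better determined: no table is the likelier outcome at any assumed true rate from 5% to 20%, and has a probability of about 42% even at 25%.

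These probabilities assume N = 20 and independent subjects, and the rates are illustrative. No safety data are lost, because the events remain in the general TEAE tables and listings. What is at risk is the combined subject-level cardiovascular figure that the protocol promised.

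**What to change.** 1. In SAP 12.3.3.2, report two rows whatever the number of subjects: (a) subjects with any cardiovascular AE, fatal or not, using the SMQ/SOC/HLGT list already written there for cardiovascular death; (b) subjects with adjudicated MACE. Before using the list for (a), review its less specific entries, such as the SMQs for shock-associated conditions and for arrhythmia-related investigations, signs and symptoms.
2. Drop the five-subject condition for these two proportions, so that they agree with Protocol 9.6.7. Adding the rows while keeping the condition would leave both suppressed at low counts.
3. State one adjudication scope in the Protocol synopsis, 9.1, 9.5.4.1.1.5 (opening and cardiovascular paragraph) and 9.5.5, and in the charter.
4. Record the definition and the removal of the threshold in SAP 14.

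The cost is wording in the SAP, protocol and charter, and one additional programmed row from an existing list. The drawback is that row (a) contains non-adjudicated and less specific events and may look less favourable. Showing it beside row (b) lets the reader weigh both.
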